6.3.2 Secondary Efficacy Evaluation

- (1) Evaluation Indicators
 - Number of positive cases per 1,000 catheter-days of bacterial colonization at CVC tips;
 - 2) Bacterial colonization rate at the tip of other types of (percutaneous) deep vein

catheters and the catheterization site (number of culture positive cases/total catheters x 100% and number of positive cases per 1,000 catheter-days), including hemodialysis, PICCO, float catheters, etc;

- 3) Occurrence of suspected CLABSI/CRBSI, which entails catheter tip bacterial culture and blood bacterial culture
- 4) Securement performance of the dressing: Frequency of dressing changes associated with wearing time and warping or peeling
- (2) Evaluation method

FAS and PPS were used for evaluation.

Quantitative descriptive statistics (number of cases, mean, standard deviation, median, minimum, maximum) were used to describe the number of positive cases per 1,000 catheter-days occurring in the two groups of CVC tip bacterial colonization, and t-test or rank sum test was used to compare the two groups. In addition, a mixed linear model was developed to evaluate the difference in the number of positive cases per 1,000 catheter days of bacterial colonization between the two groups, using the number of positive cases per 1,000 catheter days of bacterial colonization of the CVC tip segment after extubation as the dependent variable, group as a fixed effect, and insertion site, skin infection of baseline at the insertion site, and their interaction as random effects.

The number and percentage of cases of bacterial colonization at the tip of other types of (percutaneous) deep vein catheters and the catheterization site after extubation were described separately for both groups with the total number of catheters and at the participant level, and the two groups were compared using the chi-square test or Fisher's exact test.

Quantitative descriptive statistics (number of cases, mean, standard deviation, median, minimum, maximum) were used to describe the number of positive cases per 1,000 catheter days occurring at the tip of other types of (percutaneous) deep vein catheters and the catheterization site after extubation in both groups. If more than one catheter of the same type was placed in the same participant, it will be analyzed with the total number of catheters and participant level separately and the two groups will be compared using a t-test or Wilcoxon rank sum test.

The number of cases, case times and occurrence rate of suspected CLABSI/CRBSI occurred in the two groups of different bacteriological culture specimens types and at catheter locations were calculated, and the two groups were compared using the chi-square test or Fisher's exact test.

The number of cases, case times and occurrence rate of positive occurrences in the two groups of different bacteriological culture specimens types were summarized by bacterial classification, specific bacterial name, and the two groups were compared using the chi-square test or Fisher's exact test, respectively.

Quantitative descriptive statistics (number of cases, mean, standard deviation, median, minimum, maximum) were used to describe the duration of dressing wear in both groups and t-test or rank sum test was used to compare the two groups. The frequency of dressing changes due to edge lifting and droping out was described for both groups of participants and the two groups were compared using the chi-square test or Fisher's exact test.

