9.2 Point of Exit

Study subjects may exit the study for a variety of reasons. The Investigator shall record the reason for withdrawal and discontinuation of the study in the applicable Case Report Form. These reasons include, but are not limited to:

- Study completion (all study related visit(s) are completed)
- Withdrawal by the Subject
- Withdrawal by Investigator
- Lost to follow-up
- Death
- Study Termination

If a subject withdraws or discontinues participation before study completion, the subject will not be accounted into the per protocol set (PPS) analysis until the required enrollment is reached but will be accounted into the safety set analysis.

[figure not shown]
Data collected until the last known contact of study subject may be used in the analysis of study data. Because the subjects in this study are all ICU patients, patients will be considered lost to follow-up if they are transferred out of the ICU or discharged without removal of the CVC. If the study subject withdraws from the study for any reason and there is an ongoing safety event, additional safety event information may need to be collected by the Investigator and shared with Sponsor.

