4.1.2 Secondary efficacy indicator

- Number of positive cases per 1,000 catheter-days of bacterial colonization at the tip of the CVC (number of culture-positive catheters/total catheter retention time (days) * 1000%));
- (2) Bacterial colonization rate at the tip of other types of (percutaneous) deep vein catheters and the catheterization site (number of culture positive cases/total catheters x 100% and number of positive cases per 1,000 catheter-days), including hemodialysis, PICCO, float catheters, etc;
- (3) Occurrence of suspected CLABSI/CRBSI, which entails catheter tip bacterial culture and blood bacterial culture
- (4) Securement performance of the dressing: Frequency of dressing changes associated with wearing time and warping or peeling

participant wear time (hours) = sum of all dressing wear times (hours) for the participant/participant dressing changes

Number, where wear time (hours) for each dressing = change date time - use date time.

Replacement due to edge lifting and droping out is defined as whenever there is a dressing replacement due to edge lifting and droping out, it is determined that the participant appears to be replaced.

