6.2.2 General Information

- (1) Evaluation Indicators
 - 1) Demographic information: Age, gender, nationality, height and weight;
 - 2) General Condition: medical history, allergic history.
 - 3) Deep vein indwelling catheterization and peripheral skin evaluation status: Insertion site, insertion type, duration of insertion (days), with or without blood oozing after puncture placement, whether other products were applied, whether emergency insertion was performed, whether skin assessment around the insertion site was performed, skin assessment around the insertion site (including erythema, edema, pruritus score and whether skin infection was diagnosed);
 - ♦ Methodology for calculating relevant indicators:
 - ✓ Age (years) = (date of informed consent date of birth + 1) / 365.25, rouding to whole numbers
 - ✓ Duration of tube insertion (days) = date of randomization date of tube insertion + 1
- (2) Evaluation method

FAS was used for evaluation.

The demographic data, general conditions were described accordingly to their numerical characteristics and quantitative indicators were compared between the two groups of participants using t-test/Wilcoxon rank sum test; qualitative indicators were compared between the two groups of participants using chi-square test/Fisher exact probability method.

Summary of the evaluation of deep vein indwelling catheterization and surrounding skin at the level of the insertion site. The two groups of quantitative indicators were compared using t-test/Wilcoxon rank sum test according to their corresponding numerical characteristics description; and the two groups of qualitative indicators were compared using chi-square test/Fisher exact probability method.

In addition, a list of data on medical history, allergic history, deep vein indwelling catheterization prior to enrollment and skin evaluation around the insertion site, and previous/concomitant medication was made for both groups of participants.

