6.2.3 Exposure

6.2.3.1 Studied products

Quantitative descriptive statistics (number of cases, mean, standard deviation, median, minimum, maximum) were used to describe the study time (days) for both groups of participants. Quantitative descriptive statistics (number of cases, mean, standard deviation, median, minimum, maximum) were used to describe the total insertion time (h) and total dressing using time (h) for the two groups with different DVC catheters, respectively.

- Duration of study: Study duration is from the date of randomization to the date of completion/withdrawal from the trial when participants were studied on the study summary page.
 - ✓ Study Duration (days) = date of completion/withdrawal from trial date of randomization + 1

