7.3 Missing primary efficacy endpoint

Missing primary efficacy endpoint will be filled using the WCCF (i.e., filled as "positive"), while, at the same time, giving the result of not filling.

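### SAP 6.3.2 analyses colonization per 1,000 catheter-days with methods that need a value per catheter or participant, but SAP 4.1.2 defines only a ratio of totals

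*SAP*

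**What the plan says.** - **Definition.** SAP 4.1.2 gives the first-listed secondary indicator, the CVC-tip rate, as "number of culture-positive catheters/total catheter retention time (days" and scales it to 1,000. No unit of analysis is stated.
- **Analysis, CVC tips.** SAP 6.3.2 summarises the rate by number of cases, mean, SD, median, minimum and maximum. It then describes the rate "occurring in the two groups of CVC tip bacterial colonization, and t-test or rank sum test was used to compare the two groups". It also states that "a mixed linear model was developed to evaluate the difference in the number of positive cases per 1,000 catheter days", with the rate as dependent variable, group as fixed effect, and insertion site, baseline skin infection and their interaction as random effects.
- **Analysis, other DVC types.** The rate covers tip and catheterization site. Where a participant has more than one catheter of a type, "it will be analyzed with the total number of catheters and participant level separately and the two groups will be compared using a t-test" or a Wilcoxon rank-sum test. This names the level but gives no formula for the individual value.
- **Missing data.** SAP 6.1 leaves missing data unfilled unless a separate section says otherwise. The only efficacy fill is SAP 7.3: "Missing primary efficacy endpoint will be filled using the WCCF".
- **Table shells.** SAP section 9 places tables, graphs and lists in a separate file.

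**The concern.** A t-test, a rank-sum test, a standard deviation and a linear mixed model all operate on a set of individual values. A ratio of totals supplies one number per arm. The programmer must therefore invent the individual value, and the SAP text gives no rule for it.

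Together with the matching rate for other DVC types, this is the only colonization comparison expressed per catheter-day. Its purpose is to account for exposure time. If the individual value is chosen without care, the reported mean is no longer the defined rate and the test may hardly use exposure time.

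**Working it through.** **Inputs from the documents.** Control tip colonization 18.7% and a 50% reduction, so 9.35% in the test arm; 220 per arm (SAP 3.2). Two-sided threshold 0.048 (SAP 6.1). Participation of about 3-14 days (SAP 3.4). The documents give no figure for this endpoint, so there is none to reproduce.

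**Assumptions, not in the documents.** Catheter dwell T uniform on the whole days 3 to 14, the same in both arms; one catheter per patient.

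**1. One ratio per arm.** Two numbers with no within-arm spread: no SD, t-test, rank-sum test or mixed model can be computed.

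**2. One value per catheter.** The obvious choice is 0 if negative and 1000/T if positive. A positive at day 3 scores 1000/3 = 333.3; one at day 14 scores 1000/14 = 71.4. Small example: dwell of 3, 3, 14 and 14 days, with one positive at each duration.
- Defined rate: 1000 × 2/34 = 58.8.
- Mean of individual values: (333.3 + 71.4)/4 = 101.2.

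**3. At the SAP's control rate.** E[T] = 8.5 and E[1/T] = 0.1460. The defined rate is 1000 × 0.187/8.5 = 22.0 per 1,000 days. The mean of individual values is 1000 × E[p(T)/T], with p(T) calibrated so that E[p(T)] = 0.187:

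| Risk of a positive tip | p(T) | Mean of individual values | Defined rate |
|---|---|---|---|
| Unrelated to dwell | 0.187 | 187 × 0.1460 = 27.3 | 22.0 |
| Constant daily hazard | 1 − exp(−0.02479 T) | 22.4 | 22.0 |
| Rising with dwell squared | 1 − exp(−0.002599 T²) | 19.3 | 22.0 |

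**4. What the other summaries show.** The median is 0 whenever fewer than half the catheters are positive. At 18.7% positive, 81.3% of catheters score 0 whatever their dwell, so the days of negative catheters, most of the denominator in SAP 4.1.2, do not enter. The rank-sum test then mainly compares proportions positive: its decision agreed with the chi-square test in 91-99% of simulated trials.

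**5. Operating characteristics by simulation** (220 per arm, threshold 0.048, equal dwell; ranges run over the three risk patterns).
- No dressing effect: rank-sum, t-test and robust Poisson reject in 4.2-5.1%.
- Risk halved to 9.35%: power is about 70-76% for the t-test, 80-82% for rank-sum and 79-82% for robust Poisson.
- The linear mixed model, simulated with a random intercept for insertion site only and no site effect, stayed within 0.1 percentage points of the t-test wherever both were run. The full random-effects structure of SAP 6.3.2 was not simulated.

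**The case against.** **The authors plainly meant a per-catheter value.** The mean/SD/median summary and the insertion-site random effect point that way, and one sentence defining the unit would make the tests runnable. The table shells may already contain it. This is fair, and it removes any claim that the analysis cannot be done. It does not remove the mismatch, because the mean of those values is still not the rate in SAP 4.1.2.

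**The SAP's tests perform adequately.** With equal dwell every option keeps its level, and rank-sum, which the SAP allows, loses no power against Poisson. This stands. A reader might infer false positives from arms with different dwell, but no section predicts different dwell. If it occurred, no method would be safe throughout: with two days' shorter dwell in one arm, risk unrelated to dwell and no dressing effect, robust Poisson itself rejects in about 20-25%.

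**The start of catheter-days.** A reader might infer that it is left open, since SAP 6.2.2 has "Duration of tube insertion (days) = date of randomization" minus the insertion date, plus one, and SAP 6.2.3.1 counts study duration "from the date of randomization to the date of completion/withdrawal from the trial". The first is a baseline descriptor and the second is time on study. The retention time in SAP 4.1.2 matches total placement time, which Protocol 10.2.4 and SAP 6.2.3.1 keep apart from dressing time. The documents point to insertion.

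**Patients who leave with the catheter in place.** Protocol 9.2 says "patients will be considered lost to follow-up if they are transferred out of the ICU or discharged without removal of the CVC". A reader might infer that their tips count as positive in this rate. SAP 7.3 names only the primary endpoint, and the SAP 6.1 default leaves other missing data unfilled. What stays open is whether their days remain in the denominator. If 10% leave this way (assumed, same mean dwell), the rate is 22.0 with these catheters left out, and 1000 × 0.187 × 0.9/8.5 = 19.8 if only their days count.

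**Poisson with few events.** With an assumed 30 catheters per arm and no dressing effect, robust Poisson rejected in only 0.2-2.2%, against 4.3-4.8% for rank-sum. The fix for other DVC types must allow for this.

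**Conclusion.** The point holds as a mismatch between a defined rate and its analysis. The SAP text defines a ratio of totals, analyses it with methods for individual values, and does not define those values. Under the assumed 3-14 day dwell, the reported mean could be 27.3, 22.4 or 19.3 where the defined rate is 22.0, and the rank-sum test would largely repeat the comparison of proportions.

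The sizes rest on the assumed dwell distribution and one catheter per patient. The gap nearly closes under a constant daily hazard and grows as risk departs from it.

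The documents do not support reading this as inflated error or as lost power in general. Only the t-test, and by extension the linear mixed model, gives up power. The primary analysis and sample size are untouched. The change should be made before database lock, while it cannot be influenced by the data.

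**What to change.** **SAP 4.1.2:** *The rate is computed per arm as culture-positive catheters divided by total catheter-days, times 1,000, with catheter-days from insertion to removal. As under SAP 6.1, a missing tip culture is not filled for this rate; that catheter is left out of numerator and denominator.* The percent sign printed after 1000 should go.

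**SAP 6.3.2, CVC tips:** *Arms are compared by the rate ratio with 95% CI from a Poisson model of catheter positivity with log(catheter-days) as offset, group as fixed effect and robust variance clustered on participant.* This replaces the mean/SD/median summary, the t-test or rank-sum test, and the linear mixed model for this rate. Any model adjusted for insertion site and baseline skin infection uses the same binary outcome and offset.

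**SAP 6.3.2, other DVC types:** use the same definition and model, separately for tip and catheterization-site positivity. Keep the participant-level analysis (any positive, summed catheter-days). Where positives are few, give an exact conditional CI for the rate ratio, noting that it ignores clustering.

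**Cost:** SAP wording and one changed model. Placement duration and cultures are already collected at the end-of-treatment visit (Protocol 10.2.4), so no new CRF item appears necessary.

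**Downside:** the offset assumes a constant daily rate. If risk does not scale with dwell and dwell differs between arms, the rate ratio can depart from 1 without a dressing effect. Report dwell by arm and read the rate ratio beside the per-catheter proportion.

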5.2 Secondary Objective(s)

The secondary objective of this study is to compare the differences in the following indicators between the test and control groups:

- Number of positive cases per 1,000 catheter-days of bacterial colonization at CVC tips
- Bacterial colonization rate at the tip of other types of (percutaneous) deep vein catheters and the catheterization site (number of culture positive cases/total catheters \times 100% and number of positive cases per 1,000 catheter-days), including hemodialysis, PICCO, float catheters, etc.

- Incidence rate of Central Line Associated Bloodstream Infections (CLABSI) or Catheter Related Blood Stream Infections (CRBSI)
- Type of pathogenic microorganism (G+/G-/fungal or specific species, drug-resistant bacteria, etc.) and percentage of positivity
- Securement performance of the dressing: Frequency of dressing changes associated with wear time and lift or drop-off
- Effects on the skin of the covered area, e.g. local infection, local skin irritation.

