5.3.2 Secondary Endpoint(s)

Removal of other types of DVCs, such as hemodialysis and PICCO to perform catheter-tip culture and sampling and culture of bacteria from skin around the insertion site;

Occurrence of suspected CLABSI/CRBSI, performing catheter-tip culture and blood bacterial culture;

Dressing securement performance, such as lift or drop-off;

Safety indicators, mainly referring to the effect of the dressing on the state of the skin.

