10.2.4 End-of-treatment Visit

Visit following the completion of dressing securement at the insertion site after removal of DVC. A patient who has multiple catheters withdrawn during the trial should be documented sequentially, but the trial is not to be considered complete at least until the CVC is removed. If replacement of the same type of DVC is performed, only the first removal is recorded and the subsequent replacement is not included in the test or observation.

The following procedures will be completed during the end-of-treatment visit:

1. Assessment of dressing securement performance;
2. Assessment of skin conditions around the catheter site, with reference to the standards for evaluating local skin irritation as listed in the appendix;
3. Photographic documentation of any anomalies;
4. Following departmental routine practice, the tip is cut with sterile scissors after removal, while skin sampling around the insertion site is performed. The samples taken are, under aseptic conditions, sent for pathogenic bacteria testing and species analysis.
5. In case of suspected CLABSI/CRBSI occurrence, sampling and quantitative culture for both catheter and peripheral blood will be performed simultaneously, as well as analysis of pathogenic bacteria species, according to diagnostic evaluation criteria.

The following data will be collected during the end-of-treatment visit:

1. Vital signs: Pulse, blood pressure, respiratory rate, body temperature;
2. Relevant laboratory tests, including blood routine examination: Red blood cell (RBC) count, white blood cell (WBC) count, neutrophil ratio, hemoglobin, platelets, C-reactive protein, etc.;
3. Documentation of dressing securement performance;
4. Documentation of skin conditions around the catheter site, including erythema, edema, rash, etc., and scoring with reference to the standards for evaluating local skin irritation as listed in the appendix.

5. Total duration of DVC placement and duration of application of the test/control dressing;
6. Catheter-tip culture and classification of colonies;
7. Culture and classification of colonies from the skin samples around the insertion site;
8. Any changes in medication use relevant to the trial, including mainly fat emulsions, heparin, blood transfusions and antimicrobial drugs;
9. Confirmation of CLABSI/CRBSI diagnosis;
10. Adverse events, device defects, complaints.

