19.4 Statistical Analyses

For patient baseline characteristics and demographic data, quantitative data will be analyzed based on t-test or rank sum test, and qualitative information will be analyzed based on Chi-square test or Fisher's exact test. CVC tip bacterial colonization rates, PICCO/hemodialysis catheter bacterial colonization rates, catheter-related bloodstream infection rates, and microbial species analysis will be analyzed by chi-square test or Fisher's exact test. Other results collected in this study, such as wearing duration, frequency of replacement, skin condition, and number of deaths, will be analyzed using t-tests or rank sum tests accordingly. The O'Brien-Fleming expenditure function will be used twice in succession to determine the test boundaries.

In addition, descriptive summaries of effectiveness and safety evaluation indicators will be presented for the entire trial and for subjects in each group. For continuous data, the data will be summarized by number of subjects, mean, standard deviation (SD), median, minimum and maximum values. For categorical data, they will be summarized by frequency and corresponding percentage.

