Appendix B

Evaluation Criteria

CLABSI/CRBSI evaluation criteria

CLABSIs: Primary bloodstream infections in hospitalized patients occur during the use or within 48 hours after removal of indwelling central venous catheters and are unrelated to the presence of infections at other sites. CRBSI: Catheter-induced bloodstream infections are primary infections that occur in patients with a central venous catheter and where there is laboratory evidence that the catheter is the source of the bloodstream infection.

Patients who develop infection symptoms such as fever, chills, and/or hypotension after catheterization and at least one peripheral venous blood culture positive of bacteremia or fungemia without any other obvious sources of bloodstream infection show one of the following: semi-quantitative catheter-tip culture ≥ 15 cfu, while the same microorganism (species) is isolated from both the catheter-tip culture and the peripheral blood culture; the ratio of bacterial growth (cfu/ml) between quantitative catheter-tip and peripheral blood cultures, which are performed concurrently, is greater than 3:1; the positive alarm time of the blood specimen is more than 2 hours earlier than that of the peripheral equivalent specimen.

Diagnostic criteria

a. Retain the catheter:

If two sets of blood cultures are positive and present the same species

- In the absence of evidence of other infections, it indicates possible CRBSI;
- If the same pathogen is found in both sets of cultures and the blood culture from the catheter reports positive 120 minutes earlier than the one from the peripheral vein: It indicates CRBSI if there is no evidence of other infections (it may also indicate CRBSI if the difference in time to positivity between the two sets of blood cultures is less than 120 minutes but have the same identification and drug sensitivity results).
- If both sets of blood cultures are positive, and the bacterial count from catheter blood cultures is at least five times higher than that of peripheral venous blood cultures,

it indicates possible CRBSI (for manual quantitative blood culture systems) if there is no evidence of other infections.

If only the catheter blood culture tests positive: It will not be a conclusive evidence of CRBSI, but may be due to bacterial colonization or contamination during blood specimen collection.

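### The bloodstream-infection endpoint is defined inconsistently: the objective is CLABSI/CRBSI incidence, but the endpoint wording and the SAP's between-group test count suspected cases

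*SAP*

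**What the plan says.** **Objective.** Protocol 5.2 and SAP 2.2 list "Incidence rate of Central Line Associated Bloodstream Infections (CLABSI) or Catheter Related Blood Stream Infections (CRBSI" as a secondary objective, with no mention of suspicion.

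**Endpoint.** Protocol 5.3.2, and the synopsis with it, defines the matching endpoint as "Occurrence of suspected CLABSI/CRBSI, performing catheter-tip culture and blood bacterial culture". SAP 4.1.2(3) and 6.3.2 carry this over as "Occurrence of suspected CLABSI/CRBSI, which entails catheter tip bacterial culture and blood bacterial culture".

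**Analysis.** Protocol 19.4 states that "catheter-related bloodstream infection rates, and microbial species analysis will be analyzed by chi-square test or Fisher's exact test". SAP 6.3.2 applies the same tests to the "occurrence rate of suspected CLABSI/CRBSI occurred in the two groups of different bacteriological culture specimens types", in the FAS and PPS.

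**Data collected.** Protocol 10.2.4 treats suspicion and diagnosis as two steps. First: "In case of suspected CLABSI/CRBSI occurrence, sampling and quantitative culture for both catheter and peripheral blood will be performed simultaneously". Then, as a separate data item: "Confirmation of CLABSI/CRBSI diagnosis". Appendix B supplies the "CLABSI/CRBSI evaluation criteria".

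**Blinding.** Protocol 4.1.1 says that neither investigators nor subjects can be blinded. Neither document describes adjudication of infections blinded to group.

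**The concern.** The infection result should estimate how often patients develop CLABSI or CRBSI under each dressing. As the SAP is written, a programmer would count patients in whom infection was suspected. That is a different quantity in two ways.

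- It includes patients whose cultures later rule infection out. If false suspicion is equally common in both groups, these patients pull the risk ratio towards 1.
- The decision to suspect is made by staff who can see the dressing. If that knowledge alters their threshold, the groups can differ in suspected cases with no difference in infection.

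This is a secondary endpoint, but bloodstream infection is the clinical event that the dressing is meant to reduce.

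**Working it through.** **Step 1: the passages side by side.**

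| Place | Event named | Planned comparison |
|---|---|---|
| Protocol 5.2, SAP 2.2 (objective) | CLABSI or CRBSI | Difference between groups |
| Protocol synopsis and 5.3.2 (endpoint) | Suspected CLABSI/CRBSI | None stated there |
| Protocol 19.4 | Catheter-related bloodstream infection | Chi-square or Fisher |
| SAP 4.1.2(3), 6.3.2 | Suspected CLABSI/CRBSI | Chi-square or Fisher, FAS and PPS |
| SAP 6.3.2, following paragraph | Positive cultures by specimen type and organism | Chi-square or Fisher |
| SAP 6.4 | TEAEs that are CLABSI; TEAEs that are CRBSI | Tabulated in the safety set, no test stated |

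The rows disagree on the event. No SAP row is a between-group test of diagnosed infection.

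**Step 2: follow one case.** A patient is suspected of CRBSI, cultures are taken, and all are negative. Appendix B classes this as *Not CRBSI*. Under the SAP 6.3.2 wording it is still an event. The same holds for a positive tip with negative blood cultures, which Appendix B calls colonization. The SAP does not define suspicion, does not cite Appendix B, and uses the confirmation item in no efficacy analysis.

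**Step 3: illustrate the size.** The documents give no design figure for infection, so this is illustration only.

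Inputs from the documents:
- 220 per group (Protocol 19.2, SAP 3.2). This is the primary-endpoint figure. For 18.7% v 9.35% and 80% power, the usual two-proportion formula without continuity correction gives 216 at two-sided 0.05 and 219 at 0.048; with the correction it gives 237 and 239. Here 220 serves only as the group size.
- Two-sided significance level 0.048 (SAP 6.1).
- A CRBSI rate of 3-5% of catheterizations (Protocol 2.0). The central value used is c = 4%.

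Assumptions:
- The test dressing halves CRBSI. The documents' 50% reduction concerns tip colonization.
- A proportion u of each group is suspected without infection, with u from 5% to 15%.

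Risk ratio for suspected cases = (c/2 + u) / (c + u). Power is the exact power of the uncorrected chi-square test.

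| u | Control v test | Risk ratio | Power |
|---|---|---|---|
| 0 | 4% v 2% | 0.02/0.04 = 0.50 | 21% |
| 5% | 9% v 7% | 0.07/0.09 = 0.78 | 12% |
| 10% | 14% v 12% | 0.12/0.14 = 0.86 | 9% |
| 15% | 19% v 17% | 0.17/0.19 = 0.89 | 8% |

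The absolute difference stays at 2 points throughout. The ratio and the precision are what suffer. At u = 5%, 220 × (0.09 + 0.07) = 35.2 cases are expected, of which 220 × (0.04 + 0.02) = 13.2 are infections.

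Over the whole 3-5% range (normal approximation), power is 18-27% with no false suspicion. With u of 5-15% the risk ratio is 0.75-0.92 and power 6-15%.

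**Step 4: differential suspicion.** Assume no true difference in infection, control suspicion of 10-25%, and 20-30% fewer suspicions in the test group. The chance of a significant result favouring the test dressing is then about 11% (10% v 8%) to 48% (25% v 17.5%). The nominal chance in that direction is 0.048/2 = 2.4%.

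**The case against.** A reader might infer that the SAP swapped the protocol's endpoint for a softer one. The documents do not support that. The word *suspected* is already in the protocol's synopsis and section 5.3.2, and the SAP repeats it. The conflict starts inside the protocol, and editing the SAP alone would leave it contradicting the protocol's endpoint.

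A reader might also infer that bare suspicion is the only infection-related comparison between groups. That is too strong. The suspected-case indicator comes with tip and blood cultures. The next paragraph of SAP 6.3.2 tests culture positivity by specimen type and organism, and blood culture is a study specimen. SAP 6.4 tabulates CLABSI and CRBSI separately. Nothing says that the Protocol 19.4 test is withdrawn, and SAP 9 describes the SAP as adding technical detail to the protocol.

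These points narrow the concern without removing it. A positive culture is not a diagnosis: Appendix B generally asks for a concordant catheter result and no other source. The SAP 6.4 table is in the safety set, which requires the catheter in place for more than 24 hours, and it has no stated test and no link to the confirmation item. The Protocol 19.4 test has no counterpart in the SAP on diagnosed cases.

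Two further objections stand. Diagnosis also depends on suspicion having prompted cultures, so counting diagnosed cases reduces ascertainment bias but does not abolish it. And *suspected* may be loose translation for diagnosed cases; if so, the correction is a clarifying sentence, but it is still needed.

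**Conclusion.** The protocol and SAP are inconsistent on the bloodstream-infection endpoint. As written, the SAP's between-group test counts cases that Appendix B would reject, in a trial where the staff raising the suspicion know the dressing. This should be corrected before analysis.

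The size cannot be fixed from the documents. The move in risk ratio from 0.50 to 0.78-0.89, and in power from 21% to 8-12%, depends on the assumed halving of CRBSI and the assumed 5-15% false suspicion. The 3-5% background rate is general, while EC-3 and EC-7 exclude patients judged at high risk of CLABSI or bloodstream infection, so the trial's own rate may differ. The differential-suspicion figures show what could happen; nothing in the documents shows that suspicion will differ by group.

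Nor should the power figures be read as saying that the change rescues the test. Power is low with either definition. The gain is an estimate that answers the stated objective and is less open to ascertainment bias.

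**What to change.** 1. In the Protocol synopsis and 5.3.2, and in SAP 4.1.2(3) and 6.3.2, make diagnosed CLABSI and diagnosed CRBSI the events. Count them separately and per subject, and compare them in the FAS and PPS with the tests already planned.
2. Derive both from the confirmation item in Protocol 10.2.4 and the Appendix B criteria.
3. State in advance which Appendix B grades (*Indicating*, *Possible*, *Cannot be determined*) count as CRBSI events. This is essential because *confirmed* is not a grade there, and for removed catheters the highest grade in the reference table is *Possible CRBSI*. For retained catheters, text and table also disagree on *Staphylococcus aureus* or *Candida* grown only from the peripheral sample (*possible* in the text, *Indicating* in the table) and must be reconciled. CLABSI has a definition in Appendix B but no grades, so the SAP should cite that definition.
4. Keep suspected cases as a descriptive line by group. A gap between suspected and diagnosed counts that differs by group would then be visible.

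The cost is wording in both documents, with the protocol change handled under Protocol 21.0. No new data are needed: cultures and the confirmation item are already collected. Having the grades assigned by someone unaware of the group would reduce bias further, at some extra effort, but the correction does not depend on it.
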